7.1 Sample Collection

At the above-mentioned visits, up to 5 mL of blood will be collected in tubes provided by or recommended by the Sponsor.

At the above-mentioned visits, nasal swab samples will be collected and transferred into tubes provided by or recommended by the Sponsor. Staff collecting the samples should use adequate infection prevention and control measures, as described in the Operating Guidelines.

Immediately prior to the blood draw or nasal swab, the staff member performing the procedure will verify the participant's identity as well as the assigned participant's number and sampling stage on the pre-printed label and will attach the label to the tube.

7.2 Sample Preparation

Serum Samples

Detailed instructions on how to prepare blood samples for assessment of immune response are contained in the Operating Guidelines provided to the site. An overview of the procedures is provided here.

Following the blood draw, the tubes are to be left undisturbed, positioned vertically and not shaken, for a minimum of 1 hour and a maximum of 24 hours to allow the blood to clot. Samples can be stored at room temperature for up to 2 hours; beyond 2 hours, they must be refrigerated at a temperature of +2°C to +8°C (+35.6°F to +46.4°F) after the period of clotting at room temperature and must be centrifuged within a maximum of 24 hours.

The samples are then centrifuged, and the serum is transferred to the appropriate number of aliquoting tubes. These tubes are pre-labeled with adhesive labels that identify the study code, the participant's number and the sampling stage or visit number.

The participant's number and the date of sampling, the number of aliquots obtained, the date and time of preparation, and the participant's consent for future use of his / her samples are to be specified on a sample identification list and recorded in the source document. Space is provided on this list for comments on the quality of samples.

Nasal Swab Samples

Detailed instructions on how to collect nasal swab samples in appropriate viral transport media for viral shedding assay(s) are contained in the Operating Guidelines provided to the site.

The participant's identification number and any other required information, the date of sampling, and the date and time of preparation will be clearly documented.

7.3 Sample Storage and Shipment

Serum Samples

During storage, serum tubes are to be kept in a freezer whose temperature is set and maintained at -20°C (-4°F) or below. The temperature will be monitored and documented on the appropriate form during the entire study. If it rises above -10°C (14°F) for any period of time, the Clinical Logistics Coordinator must be notified. See the Operating Guidelines for further details.

Shipments to the laboratories will be made only after appropriate monitoring and following notification of the Clinical Logistics Coordinator. Sera will be shipped frozen, using dry ice to maintain them in a frozen state, in the packaging container provided by the carrier. Again, temperatures will be monitored. Shipments must be compliant with the United Nations (UN) Class 6.2 specifications and the International Air Transport Association (IATA) 602 packaging instructions.

Samples will be shipped to Sample, Reagent, & Animal Services within R&D Global Operations at Sanofi Pasteur. The address is provided in the Operating Guidelines.

Nasal Swab Samples

Nasal swab samples will be shipped frozen, using dry ice to maintain them in a frozen state, in the packaging container provided by the carrier. Detailed instructions for the storage of nasal swab samples at study site and shipment of nasal swab samples to testing laboratory are contained in the Operating Guidelines provided to the site.

7.4 Future Use of Stored Biological Samples for Research

Any unused part of the serum samples and nasal swab samples will be securely stored at SRAS within Global Research Office (GRO) at Sanofi Pasteur for at least 25 years after the end of the study. These samples are being retained in long-term storage to support answers to regulatory questions related to the product's licensure and the potential revalidation of the study results. In addition, these samples will also be used for assay development activities related to RSV or other respiratory pathogens.

The other biological samples collected to qualify the participants for inclusion in the study or to monitor their health are dedicated for immediate use. In case they are not completely used up, they will be destroyed at the latest at the end of the study or after the time requested by local law.

In addition, parents / guardians / legally authorized representatives will be asked to indicate in the ICF whether they will permit the future use of any unused stored serum samples for other tests. If they refuse permission, the samples will not be used for any testing other than that directly related to this study. If they agree to this use, they will not be paid for giving permission. Anonymity of samples will be ensured. The aim of any possible future research is unknown today and may not be related to this particular study. It may be to improve the knowledge of vaccines or infectious diseases, or to improve existing tests or develop new tests to assess vaccines. Human genetic tests will never be performed on these samples without specific individual informed consent.

8 Clinical Supplies

Sanofi Pasteur will supply the study sites with protocols, ICFs, CRBs, SAE reporting forms, diary cards, memory aids and other study documents, as well as with the following study materials: all study vaccines including the device for vaccine administration, blood collection tubes, cryotubes, cryotube storage boxes, cryotube labels, temperature recorders, shipping containers, and digital thermometers.

The means for performing Electronic Data Capture (EDC) will be defined by Sanofi Pasteur. If a computer is provided by Sanofi Pasteur, it will be retrieved at the end of the study.

The Investigator will supply all vaccination supplies, phlebotomy, and centrifugation equipment, including biohazard and / or safety supplies. The biohazard and safety supplies include needles and syringes, examination gloves, laboratory coats, sharps disposal containers, and absorbent countertop paper. The site will ensure that all biohazard wastes are autoclaved and disposed of in accordance with local practices. The Investigator will also supply appropriate space in a temperature-monitored refrigerator for the storage of the products and for the blood samples, and appropriate space in a temperature-monitored freezer for serum aliquots.

In the event that additional supplies are required, study staff must contact Sanofi Pasteur, indicating the quantity required. Contact information is provided in the Operating Guidelines.

9 Endpoints and Assessment Methods

9.1 Primary Endpoints and Assessment Methods

9.1.1 Safety

9.1.1.1 Safety Definitions

The following definitions are taken from the ICH E2A Guideline for Clinical Safety Data Management: Definitions and Standards for Expedited Reporting.

Adverse Event (AE):

An AE is any untoward medical occurrence in a patient or in a clinical investigation participant administered a medicinal product and which does not necessarily have a causal relationship with this treatment. An AE can therefore be any unfavorable and unintended sign (including an abnormal laboratory finding, for example), symptom or disease temporally associated with the use of a medicinal product, whether or not considered related to the medicinal product.

Therefore, an AE may be:

- A new illness
- The worsening of a pre-existing condition
- An effect of the vaccination, including the comparator
- A combination of the above

All AEs include serious and non-serious AEs.

Surgical procedures are not AEs; they are the actions taken to treat a medical condition. It is the condition leading to the action taken that is the AE (if it occurs during the study period).

Pre-existing medical conditions are not to be reported as AEs. However, if a pre-existing medical condition worsens following study interventions in frequency or intensity, or if according to the Investigator there is a change in its clinical significance, this change should be reported as an AE (exacerbation). This applies equally to recurring episodes of pre-existing conditions (e.g., asthma) if the frequency or intensity increases post-vaccination.

Serious Adverse Event (SAE):

Serious and *severe* are not synonymous. The term *severe* is often used to describe the intensity of a specific event as corresponding to Grade 3. This is not the same as *serious*, which is based on participant / event outcome or action criteria usually associated with events that pose a threat to a participant's life or functioning. Seriousness, not severity, serves as a guide for defining regulatory reporting obligations.

An SAE is any untoward medical occurrence that at any dose

- Results in death
- Is life-threatening^a
- Requires inpatient hospitalization or prolongation of existing hospitalization^b
- Results in persistent or significant disability / incapacity^c
- Is a congenital anomaly / birth defect
- Is an important medical event (IME)

Medical and scientific judgment should be exercised in deciding whether expedited reporting is appropriate in other situations, such as IMEs that may not be immediately life-threatening or result in death or hospitalization but may jeopardize the health of the participant or may require intervention to prevent one of the other outcomes listed in the definition above. These IMEs should also usually be considered serious. Examples of such events include allergic bronchospasm requiring intensive treatment in an emergency room or at home, blood dyscrasias or convulsions that do not result in inpatient hospitalization, or the development of drug dependency or drug abuse, new-onset diabetes, or auto-immune disease.

^a The term “life-threatening” refers to an event in which the participant was at risk of death at the time of the event; it does not refer to an event which hypothetically might have caused death if it were more severe.

^b All medical events leading to hospitalizations will be recorded and reported as SAEs, with the exception of: hospitalization planned before inclusion into the study or outpatient treatment with no hospitalization.

^c “Persistent or significant disability or incapacity” means that there is a substantial disruption of a person’s ability to carry out normal life functions.

Adverse Reaction:

All noxious and unintended responses to a medicinal product related to any dose should be considered adverse reactions (AR).

(The phrase “responses to a medicinal product” means that a causal relationship between a medicinal product and an AE is at least a reasonable possibility)

The following additional definitions are used by Sanofi Pasteur:

Immediate Event/Reaction:

Immediate events are recorded to capture medically relevant unsolicited systemic AEs (including those related to the product administered) that occur within the first 30 minutes after vaccination.

Solicited Reaction:

A solicited reaction is an “expected” adverse reaction (sign or symptom) observed and reported under the conditions (nature and onset) pre-listed in the protocol and CRB (e.g., fever and runny nose occurring between D0 and D28 post-vaccination).

By definition, solicited reactions are to be considered as being related to the product administered. For vaccines administered nasally, solicited reactions can either be solicited administration site reactions or solicited systemic reactions.

Unsolicited AE / AR:

An unsolicited AE is an observed AE that does not fulfill the conditions pre-listed in the CRB in terms of diagnosis and/or onset window post-vaccination. For example, if fever between D0 and D28 is a solicited reaction (i.e., pre-listed in the protocol and CRB), then a fever starting on D28 is a solicited reaction, whereas fever starting on D29 post-vaccination is an unsolicited AE. Unsolicited AEs includes both serious (SAEs) and non-serious unsolicited AEs.

Medically Attended AE (MAAE):

An MAAE is a new onset or a worsening of a condition that prompts the participant or participant’s parent / guardian/ legally authorized representative to seek unplanned medical advice at a physician’s office or Emergency Department. A physician contact made over the phone or by e-mail will be considered a physician office visit for the purpose of MAAE collection. This definition excludes pre-planned medical office visits for routine medical care, as well as pediatric check-ups or follow-up visits of chronic conditions with an onset prior to entry in the study. An AE discovered during a planned routine visit (e.g., upper respiratory tract infection, otitis) will be collected as an MAAE.

Administration Site Reaction:

An administration site reaction is an AR at and around the administration site i.e., the intranasal mucosa. They are considered related to the product administered.

Systemic AE:

Systemic AEs are all AEs that are not injection or administration site reactions. They therefore include systemic manifestations such as headache, fever, as well as localized or topical

manifestations that are not associated with the vaccination or administration site (e.g., conjunctivitis that is localized but that is not occurring at the administration site).

Adverse Event of Special Interest (AESI):

An adverse event of special interest is one of scientific and medical concern specific to the Sponsor's product or program, for which ongoing monitoring and rapid communication by the investigator to the sponsor can be appropriate. Such an event might warrant further investigation in order to characterize and understand it. Depending on the nature of the event, rapid communication by the study Sponsor to other parties (e.g., regulators) might also be warranted. AESIs include both serious (SAEs) and non-serious unsolicited AEs.

The following definitions are for the different phases of safety follow post-vaccine administration:

Acute Phase:

The Acute Phase begins with vaccine administration on D0 and ends at midnight on the 28th day after vaccine administration (D28). The Acute Phase for the second vaccine administration begins on D56 post-vaccination and ends at midnight on D84

During the Acute Phase of the study, a study healthcare professional will be available by telephone 24 hours a day for consultation with parents / guardians / legally authorized representatives regarding any illnesses that may occur during this period. Study personnel will have daily contact with the parents / guardians / legally authorized representatives for the first 7 days after each vaccine administration and then 3 times weekly after Day 07 up to 28 days after each vaccine administration. This 28-day Acute Phase of safety follow-up is consistent with the duration of shedding of live-attenuated RSV viruses in RSV seronegative infants and toddlers (5) (6). If the parent / guardian/ legally authorized representative reports an SAE, a safety event that meets the study pause or stop criteria ([Section 5.1.6](#)), or symptoms suggestive of a respiratory tract illness, then an illness visit should be scheduled ([Section 5.1.4, Table 5-4](#)). During the Acute Phase, the eDC allows daily safety monitoring of the study participant and will be programmed to send an alert to the parent / guardian / legally authorized representative and study site when there are symptoms suggestive of respiratory tract illness ([Table 5-4](#)).

Post-Acute Phase:

The Post-Acute Phase for participants receiving 1 administration begins at 12:01am on D29 and ends at midnight on D56. The first Post-Acute Phase for participants receiving 2 administrations begins at 12:01am on D29 and ends at midnight on D56, except if second administration is exactly on D56 when it ends immediately before receipt of the second administration. The second Post-Acute Phase for participants receiving 2 administrations begins at 12:01am on D85 and ends at midnight on D112.

During the Post-Acute Phase of the study, parents / guardians / legally authorized representatives will be instructed to monitor for and contact study staff if their child has had symptoms that are suggestive of a serious adverse event. If the parent / guardian / legally authorized representative reports an SAE or safety event that meets the study pause or stop criteria ([Section 5.1.6](#)), then an illness visit should be scheduled ([Section 5.1.4, Table 5-4](#)).

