Phase I/II Study, 6 Planned Visits, 40 (42) Non-visit Telephone Contacts, 2 Vaccinations, 4 Planned Blood Samples, 2 Planned Nasal Swabs, up to a Maximum of 12 Months of Participation per Participant

Visit (V) / Contact	Visit 03	Phone contacts 19-24	Visit 04	Phone contacts 25-30	Visit 05 ^{†††}	Phone contact 31 – 40 (42) ^{‡‡}	Visit 06 ^{‡‡}	Illness Visit(s) *** Visit 99
Study timelines – Days (D)	D56+7	Daily (x6)	D63 (+7)	Twice weekly (x6) between D64 and D83	D84 (+8)	Every 2 weeks between Visit 05 and Visit 06	1 – 31 Oct (SH) 1 – 30 Apr (NH) or > 5 months after last vaccine admin.	Any time between Visit 01 and Visit 06
In-person visit	X		X		X		X	X
Non-visit contact*		X		X		X		
Vital signs [†]	X		X		X			X
Interim history	X		X		X			X
Focused clinical examination	X		X		X			X
COVID-19 test	X							X
Collection of reportable concomitant medications/ vaccinations	X							X
Dose Number	X							
Blood samples	BL0002				BL0003		BL00P2	
Nasal swabs [‡]			NS0002					NS0002 or UN0001 to UN000X
Vaccination (2nd administration)	X							
Immediate surveillance (30 min) [§]	X							
Diary Card (DC1)	DC3							
DC / eDC reviewed**	DC2/eDC	DC3/eDC **	DC3/eDC	DC3/eDC **	DC3/eDC		X	X
DC collected	DC1/DC2				DC3			

Visit (V) / Contact	Visit 03	Phone contacts 19-24	Visit 04	Phone contacts 25-30	Visit 05 ^{†††}	Phone contact 31 – 40 (42) ^{‡‡}	Visit 06 ^{‡‡}	Illness Visit(s) *** Visit 99
Study timelines – Days (D)	D56+7	Daily (x6)	D63 (+7)	Twice weekly (x6) between D64 and D83	D84 (+8)	Every 2 weeks between Visit 05 and Visit 06	1 – 31 Oct (SH) 1 – 30 Apr (NH) or > 5 months after last vaccine admin.	Any time between Visit 01 and Visit 06
Memory aid (MA) provided					X			
MA reviewed							X	X
Collection of solicited local respiratory and systemic reactions ^{††}	X	X	X	X	X			
Collection of unsolicited adverse events ^{††}	X	X	X	X	X			
Collection of adverse events of special interest ^{††}	X	X	X	X	X			
Collection of medical attended adverse events ^{††}	X	X	X	X	X			
Collection of serious adverse events					X			

*Non-site visit contacts are to be made by phone at scheduled timepoints in the study.

† Vital signs will be collected in the eCRF.

‡ All participants will provide a nasal swab sample for quantification of vaccine virus shedding at D63, i.e., 7 days after vaccination 2. The same nasal swab specimen will also be tested for respiratory pathogens (including COVID-19), if the participant is ill at the time of D63 visit.

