All participants in each vaccine group in Cohorts 2 and 4 will provide a blood sample at the D84 visit (28 days post-vaccination 2) for the measurement of post-vaccination 2 serum antibodies to RSV.

All participants in Cohorts 1, 2, 3 and 4 will provide a blood sample during the month following the RSV season or at least 5 months after the last vaccine administration for the measurement of post-season RSV antibody titers, to determine if a 4-fold or greater rise in RSV antibody titers has occurred during the RSV season, indicating infection with wt RSV that was not detected by surveillance.

Nasal swab samples:

Nasal swab samples will be collected in all participants at D7 for Cohorts 1, 2, 3 and 4; and on D63 for Cohorts 2 and 4 for the following:

- Quantification of vaccine virus shedding on D7 for Cohorts 1, 2, 3 and 4, and D63 for Cohorts 2 and 4.
- The same nasal swab specimens will be tested for respiratory pathogens if the child is ill at the same time points (D7 for Cohorts 1, 2, 3 and 4, and D63 for Cohorts 2 and 4).

- A nasal swab specimen for the detection of RSV and respiratory pathogens will be collected from participants during illness visits and 48 hours later at any other protocol-specified time point in the study (see [Table 5-4](#)) including the medically attended surveillance during the RSV season.

Collection of Safety Data:

The Acute Phase for the first vaccine administration begins on D0 post-vaccination and ends at midnight on D28. The Acute Phase for the second vaccine administration begins on D56 post-vaccination and ends at midnight on D84. Any adverse reactions, AEs, AESIs, MAAEs, or SAEs that begin within the Acute Phase (i.e., within 28 days after a vaccination) but are diagnosed by a medical professional after 28 days will still be considered as occurring within the Acute Phase.

The Post-Acute Phase for participants receiving 1 administration begins at 12:01 am on D29 and ends at midnight on D56. The first Post-Acute Phase for participants receiving 2 administrations begins at 12:01 am on D29 and ends at midnight on D56, except if second administration is exactly on D56 when it ends immediately before receipt of the second administration. The second Post-Acute Phase for participants receiving 2 administrations begins at 12:01 am on D85 and ends at midnight on D112.

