- 11) Give or download the parent / guardian / legally authorized representative a diary card (DC3) / eDC and a thermometer and go over the instructions for their use, as detailed in the Study Operating Guideline, and remind to complete the Day 0–7 pages of DC3 / eDC. The parent / guardian / legally authorized representative will record the child's temperature and signs of illness (solicited reactions and unsolicited AEs, including AESIs, MAAEs and SAEs) on the DC3 / eDC.
- 12) Remind the parent / guardian / legally authorized representative to expect a telephone call from the study site nurse daily after this Visit 04 to review what they have entered daily in the DC3 / eDC, and to complete the entries of DC3 and bring to Visit 05 at the specified date and time.
- 13) Remind the parent / guardian / legally authorized representative to notify the site in case of an SAE or any illness. The site staff, upon evaluation, will schedule an Illness Visit within the stipulated time frame of site notification, if required.
- 14) Complete the relevant CRFs for this visit.

Post-RSV Season or ≥ 5 Months After Last Vaccine Administration Visit for All Cohorts (Visit 04 for Cohorts 1 and 3 or Visit 06 for Cohorts 2 and 4)

- 1) Obtain a blood sample for serum antibodies to RSV.
- 2) Review the MA for SAEs with the participant's parent / guardian / legally authorized representative.
- 3) If an SAE had occurred, follow the instructions in [Section 10](#) for reporting it. Remind to notify the site in case of an SAE.
- 4) Complete the relevant CRFs for this visit and the End of Study CRF.

Visit 04: D63+7 Post-Vaccination 1 (Day 07 Post-Vaccination 2) Visit Procedures for Cohorts 2 and 4

- 1) Review medical history, including past and ongoing medication since the last visit.
- 2) Perform a focused clinical examination including temperature, pulse, and respirations, EENT, respiratory, cardiac and lymphatic system.

- 3) Obtain a nasal swab sample for quantification of vaccine virus shedding. If the participant meets criteria for an Illness Visit, the same nasal swab specimens may also be tested for respiratory pathogens.
- 4) Review the solicited reactions and unsolicited AEs, AESIs, MAAEs and SAEs in the completed DC3 / eDC with the participant's parent / guardian / legally authorized representative.
- 5) If an SAE occurred, follow the instructions in [Section 10](#) for reporting it. Remind to notify the site in case of an SAE.

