5.2.7 Contraindications for Subsequent Vaccinations

5.2.7.1 Temporary Contraindications

Should a participant experience one of the conditions listed below at Day 0 (Cohorts 1, 2, 3 and 4) or Day 56 (Cohorts 2 and 4), the Investigator will postpone further vaccination until the condition is resolved. Postponement must still be within the timeframe for vaccination i.e., within 5 days of randomization for Day 0 (Cohorts 1, 2, 3 and 4) and within 7 days of Day 56 (Cohorts 2 and 4).

- 1) Any acute febrile illness (rectal temperature $\geq 38.0^{\circ}\text{C}$ [$\geq 100.4^{\circ}\text{F}$]), acute otitis media, upper and lower respiratory signs or symptoms (including but not limited to rhinorrhea, cough, and pharyngitis), or nasal congestion in the past 24 hours that according to investigator's judgment is significant enough to interfere with successful absorption of the study product.
- 2) Receipt of any of the following before any study vaccination or scheduled administration after any study vaccination:
 - any influenza vaccine within 7 days prior, or
 - any inactivated vaccine or live-attenuated rotavirus vaccine within the 14 days prior, or
 - any live vaccine, other than rotavirus vaccine, within the 28 days prior, or
 - another investigational vaccine or investigational drug within 28 days prior.

All eligible participants from the same household who are enrolled on the same date must receive the study product on the same date, and therefore if one child experiences illness as above, product administration should be deferred for both children.

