9.1.1.3.4 Medically Attended Adverse Events

Any MAAEs occurring within the first 28 days post-vaccination (D0 to D28 for all participants in Cohorts 1, 2, 3 and 4 and D56 to D84 for participants in Cohorts 2 and 4) will be collected using the same process as other AEs. Medically attended acute respiratory illness (MAARI) and medically attended acute lower respiratory illness (MAALRI) events occurring within this time frame and outside the RSV surveillance season will be classified as MAAEs.

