4.4.1.2.4 Time of Onset

Time of onset is derived from the start date of the unsolicited AE and the date of last vaccination as described in Section 4.4.1.2.3:

- start date of the unsolicited AE – date of last vaccination before the unsolicited AE

The time of onset is considered as missing only if one or both dates are missing or partially missing.

The unsolicited AEs will be analyzed “within 28 days” after each vaccination (i.e. acute phase), which corresponds to AEs with a time of onset between 0 and 28 days. An AE with missing time of onset will be considered to have occurred just after the last vaccination (computed according to the Section 4.4.1.2.3), so will be included in these tables.

Time of onset period is displayed as D0-D3, D4-D7, D8-D14, D15 or later, and Missing.

Note: Unsolicited AE that occurred before vaccination (negative time of onset) or with a time of onset higher than defined above will not be included in analysis but will be listed separately.

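### The dose-2 safety window is written both in fixed days from dose 1 and in days from the actual dose, and the two agree only when dose 2 falls on D56

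*Protocol*

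**What the plan says.** **Fixed days counted from dose 1.** Protocol Section 9.1.1.1 (repeated in Section 5.1.1 and the Synopsis): "The Acute Phase for the second vaccine administration begins on D56 post-vaccination and ends at midnight on D84". The second Post-Acute Phase then runs D85 to D112. Sections 9.1.1.3.4 (MAAEs) and 9.1.1.3.5 (AESIs) give the period in days as "D56 to D84 for participants in Cohorts 2 and 4". The diary footnote to the Vaccination 2 procedures table, and SAP Table 3.3, also use D56 to D84. The row for phone contacts 25-30 reads "Twice weekly (x6) between D64 and D83".

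**When dose 2 may be given.** Section 5.2.7.1 allows a postponed second dose "within 7 days of Day 56 (Cohorts 2 and 4"), that is, up to D63. The first Post-Acute Phase ends on D56, "except if second administration is exactly on D56 when it ends immediately before receipt of the second administration" (Section 5.1.1), so the authors foresaw other dosing days.

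**Days counted from the actual dose.** The primary safety endpoints (Section 9.1.1.2), the acute row of Table 5-4, the diary instructions (Section 9.1.1.3.2) and the unsolicited-event instructions (Section 9.1.1.3.3) all run 28 days from each vaccination. SAP Section 4.4.1.2.4 subtracts the date of the last vaccination from the event's start date and keeps the acute window, "which corresponds to AEs with a time of onset between 0 and 28 days".

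**Contacts and swab.** Section 9.1.1.1 asks for daily contact for a week, "then 3 times weekly after Day 07 up to 28 days after each vaccine administration". The second shedding swab belongs to "Visit 04: D63+7 Post-Vaccination 1 (Day 07 Post-Vaccination 2) Visit Procedures for Cohorts 2 and 4" (Section 5.1.4.1).

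**The concern.** Section 9.1.1.2 equates the 28 days after vaccination with the Acute Phase, so two definitions of that phase mean two definitions of a primary safety endpoint. A site, or whoever programs the electronic diary, could follow either. If the fixed days are followed, non-serious events late in the window of a child dosed after D56 may never be recorded. During the Post-Acute Phase, Section 9.1.1.1 asks parents to watch only for signs of a serious event.

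The analysis would not repair this. SAP Section 4.4.1.1.3 puts a child in the denominator for a solicited reaction as soon as there is one non-missing presence, and protocol Section 12.3.1 replaces nothing. A child whose diary stopped at D84 would look fully observed. Dose-2 rates could then appear lower than dose-1 rates partly because follow-up was shorter. Sparser calls after dose 2 would push the same way, and that difference does not depend on a late dose.

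The swab matters for a related reason. Section 5.1.2 says maximal replication does not typically occur until Day 7, and shedding feeds both a secondary safety endpoint and the infectivity endpoint. A dose-2 swab taken well after day 7 is not like-for-like with a dose-1 swab at D7.

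**Working it through.** **Inputs.** Acute Phase 2 runs from D56 to D84 (Section 9.1.1.1). Dose 2 is permitted on day d, from D56 to D63 (Section 5.2.7.1). Visit 04 is D63 (+7), so D63-D70. Visit 05 is D84 (+8), so D84-D92. Calls 25-30 end at D83 (procedures table).

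**Reproducing the plan's figure.** 84 - 56 = 28 days, so the fixed window equals the stated 28 days when d = 56.

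**Late dosing.** If collection stops at D84, days kept = 84 - d and days lost = d - 56. Counted from the dose, the window ends on d + 28.

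| Dose 2 on | Dose-anchored end | Kept if stopped at D84 | Lost | Share of 28 | Post-dose day at D83 |
|---|---|---|---|---|---|
| D56 | D84 | 28 | 0 | 0% | 27 |
| D57 | D85 | 27 | 1 | 3.6% | 26 |
| D60 | D88 | 24 | 4 | 14.3% | 23 |
| D63 | D91 | 21 | 7 | 25.0% | 20 |

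If Day 0 is counted as a day, the last loss is 7/29 = 24.1%. For a D63 dose, D85-D91 are post-dose days 22-28 but carry the Post-Acute 2 label.

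**Does the dose-anchored reading fit the visits?** For d = 63, d + 28 = D91, inside the Visit 05 window (to D92), and d + 7 = D70, inside the Visit 04 window (to D70). Under that reading 0 days are lost for any permitted dosing day.

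**Visit 05 footnote.** It asks for 84 days after dose 1 and 28 days after dose 2. Both hold exactly only if 84 - 28 = 56, a D56 dose.

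**Contact frequency.** After dose 1, 10 calls over D8-D28 (21 days, 3 weeks) is 10/3 = 3.3 per week, plus a D29 call. After dose 2, 6 calls over D64-D83 (20 days, 20/7 = 2.86 weeks) is 6/2.86 = 2.1 per week. The text in Sections 9.1.1.1 and 9.1.1.3.2 gives 3 per week after each dose. This affects all children with dose 2 planned: 40 (Cohort 2) + 180 (Cohort 4) = 220.

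**Swab.** The latest Visit 04 swab after an on-time dose is D70 - D56 = day 14. The dose-1 swab is scheduled at D7 with no stated tolerance. SAP Section 5.1.2.2 reports both as 7 days after vaccination and sets no swab window.

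**The case against.** The strongest reply is that D56-D84 is nominal shorthand and that most operative text follows the actual dose. Section 5.1.1 itself, straight after the D56-D84 sentence, explains the Acute Phase as 28 days after a vaccination. Section 6.7.1 does the same, and the AESI and MAAE sections put the dose-anchored rule first and the day numbers in brackets. Visit 05 is also described as Day 28+8 after vaccination 2, and Section 5.1.4.2 lets acute-phase calls run to D84+8. This largely stands, and it makes truncation a risk rather than a fact. It does not remove the conflict: the D56 exception and the D85 start of Post-Acute 2 show the fixed days used as working boundaries, and the schedule lists no call between D83 and Visit 05.

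A reader might infer that late-dosed children lose a quarter of the primary window. The documents do not support that as an outcome. It needs the fixed days to override every dose-anchored passage, and 25% applies only at D63.

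A reader might also infer that the swab is tied to D63 and could be taken on the day of a D63 dose. That contradicts the protocol, which describes the swab as 7 days after vaccination 2 and places six daily calls between the dose and Visit 04. Only late sampling survives.

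Two further replies hold. Events before a late second dose are not misattributed: SAP Section 4.4.1.2.3 assigns them by start date to dose 1, and onsets beyond 28 days are listed separately. Placebo children follow the same dose-2 schedule, so a shortened window would not obviously favour a vaccine group; absolute rates and dose-1 versus dose-2 comparisons remain exposed. Daily electronic diary monitoring and the in-person Visit 05 soften the call difference but do not settle it.

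**Conclusion.** The point holds as an inconsistency in a primary safety definition. The possible loss is 0 to 7 of 28 days per child within the permitted dosing window, and it arises only if collection actually stopped at D84. The number of children dosed after D56 is not given, so the loss across the 220 cannot be estimated. The SAP per-protocol set accepts dose 2 up to 66 days after dose 1. A D66 dose would lose 10/28 = 35.7% on the literal reading, and its 28-day end (D94) would pass the last day of Visit 05, but D66 lies outside the protocol's own dosing window.

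The contact-frequency conflict is direct and applies whatever the dosing day. The swab point is narrower: sampling up to day 14 after a D56 dose is allowed, with no matching tolerance at dose 1. None of this shows that data were lost or that shedding results are wrong. The wording should be corrected and actual timing reported; the matter falls short of a flaw that must be resolved before the primary safety results can be used.

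**What to change.** - State Acute Phase 2 and the diary, AESI and MAAE windows as the actual vaccination 2 date through day 28 after it, with Post-Acute 2 following. This applies the rule already in the endpoints and the SAP.
- Reconcile the last phone contact and the Visit 05 footnote with that date.
- Reconcile the contact-frequency passages (Sections 9.1.1.1 and 9.1.1.3.2 against the procedures table and SAP Table 3.3).
- Express the Visit 04 swab relative to the actual vaccination 2 date.
- In the SAP, report the actual post-dose day of every swab and add a sensitivity summary limited to swabs near day 7, in a band stated in advance.

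The cost is amendment wording, one date rule in the electronic diary and a small SAP addition. Compared with stopping at D84, late-dosed children would have at most 7 more diary days; doses on D56-D63 fit the existing visit windows. If collection is already well advanced, reporting each child's actual days of follow-up after dose 2 and actual swab day remains feasible.
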